**22 subjects will be recruited to each of the three arms.**

### Other Mechanism of action related endpoints

- Intestinal permeability (stool  $\alpha$ 1 antitrypsin): Previous studies have indicated that alcoholic liver disease is associated with increased intestinal permeability. We will measure intestinal permeability, as measured by the stool  $\alpha$ 1 antitrypsin level across the two study arms correcting for baseline values using analysis of covariance. We will not plan any formal hypothesis testing because there are no prior data to guide sample size estimates etc.
- Intestinal inflammation (stool lactoferrin and calprotectin, ELISA): These are considered to be markers of intestinal inflammation. They will also be analyzed using a similar approach as noted above. We will compare the levels across both arms correcting for baseline values for these continuous variables, which we anticipate will be normally distributed.
- Systemic inflammation: We will measure the following:

A: C reactive protein

B: 4-OH nonenal and malondialdehyde (oxidative stress markers)

C: cytokines: Innate immunity- TNF- $\alpha$ , IL6, Inflammasome- IL1 $\beta$ , TH1- interferon-gamma, TH2- IL-10, IL-4, Treg-IL17, IL23 (these will be run on a multiplex machine but are subject to ongoing funding from NIAAA for these analyses).

### **Null Hypothesis**

The null hypothesis is that there will be no significant differences between the steroid + placebo arm, versus either steroid + active drug arm, with respect to the plasma endotoxin level.

### **Analysis Population**

For the mechanistic endpoints, we will perform an intent-to-treat analysis. An intent to treat analysis will also be performed for the following endpoints:

- Proportion meeting Lille criteria for futility (Lille score > 0.45)
- Mortality at day 30, 90 and 180
- Change in MELD score and discriminant function adjusting at day 7 and 30 for baseline values
- Change in liver functions adjusting for baseline values on day 7 and 30.

For mechanistic and safety related endpoints, we will include an efficacy evaluable set which will only include those who have received drug for the planned duration within the study.

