**ENDPOINTS:**

*Mechanistic Endpoints:*

- The sample size is based on a decrease in plasma endotoxin levels (adjusting for baseline) as measured by analysis of covariance across the study groups. This was

chosen based on the mechanism of action of Imm 124-E. The hypothesis is that both active-drug groups are superior to placebo. In prior studies, we have found the standard deviation of endotoxin levels to be 8-10%

- markers of gut permeability
- intestinal inflammation (calprotectin)
- TNF- $\alpha$  and other immune-inflammatory markers
- microbiome-metagenome

*Efficacy related endpoints:*

- number of subjects meeting Lille failure criteria at day 7
- mortality at 30 days, 90 days and 180 days,
- time to drop in conjugated bilirubin by 50%
- change in MELD and sequential organ failure assessment scores and Discriminant Function
- serum bile acids
- liver function tests

*Safety related endpoints:*

- incidence and severity of gastrointestinal events, including nausea, vomiting and diarrhea
- Proportion of subjects who develop renal failure, encephalopathy or pulmonary compromise
- Frequency of sepsis
- Frequency of any other adverse events

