### **Exploratory Endpoints**

[figure not shown]
The exploratory endpoints will include:

- sCD14 levels (ELISA test to be measured at VCU)
- Intestinal permeability Intestinal inflammation (stool calprotectin by ELISA -to be measured at VCU)
- Proportion meeting Lille criteria for futility (Lille score > 0.45) at day 7
- Mortality at day 7, day 30, day 90 and day 180

- Change in MELD score and discriminant function
- Change in liver function
- Intestinal microbiome-metagenome (end of treatment (EOT) comparison) 
- Activation of systemic inflammation: (EOT across group comparison, baseline-EOT comparison)
  - Markers of oxidative stress (measured at IU)
  - T-cell phenotypes (measured at IU)
  - Cytokines for specific T cell subtype and activation of innate immune system (measured at IU)
- Hepatic transcriptome (real time PCR, gene array Illumina in all cases-EOT across group analyses).RNA will also be available for baseline data and gene array with PCR confirmation of key targets will be performed so that variances at baseline across groups can be accounted for.

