## INVESTIGATIONAL PLAN

### Overall Study Design and Plan – Description

**Figure 1: Study Schema**

Subjects with severe AH (MELD score  $\geq 20$  and  $\leq 28$ ) about to receive prednisolone (40 mg/day x 28 days) will be randomized to receive either:

- Group A: 2400 mg/day Imm 124-E as 1200mg bid PO
- Group B: 4800 mg/day Imm 124-E as 2400mg bid PO
- Group C: Identical appearing placebo bid PO

Treatment will be for 28 days (**Fig. 1, above**). Given variable outcomes and response to corticosteroid therapy in patients with severe AH, a Lille model was developed by French investigators to identify subjects early in the course of treatment that are unlikely to benefit from continued treatment and in fact might have worse outcome. The Lille model takes into account patient's age, and at the start of therapy total bilirubin, albumin, creatinine, prothrombin time values and total bilirubin level on day 7 of therapy. It projects a 6-month survival probability of patients with a Lille score above 0.45 to be about 25% contrary to patients with a Lille score below this cutoff (85%). Subjects who meet the Lille criteria for failure of treatment on Day 7 or side effects requiring discontinuation of steroids will be removed from the study. Standard of care nutrition support and alcohol cessation recommendations will be provided to all subjects. Alcohol withdrawal will be managed per standard of care.

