**Table 2: Schedule of Study Procedures**

Schedule of Study Procedures	Screening	Treatment Phase		Follow-up Phase		
	Day-7 to 0	D0	D7	D30	D90	D180
Informed Consent	X					
Eligibility Criteria/Demographics	X					
Medical and Surgical History/Updated	X		X	X	X	X
Medication Record /Concomitant meds	X		X	X	X	X
Physical Exam/Vital signs	X		X	X	X	X
Anthropometric Measurements/Nutrition	X					X
Urine Pregnancy Test	X		X	X	X	
Adverse Event Assessment			X	X	X	X
Liver biopsy (if performed)	X					
Study Drug Compliance Assessment			X	X		

Assessment of Meld, DF, and Child Pugh Scores	X		X	X	X	X
Assessment of Lille Score			X			
Alcohol Addiction Advice per SOC	X		X	X	X	X
Dispense Study Drug		X				
Alcohol AUDIT and NIAAA Six Question Set	X					X
Time Line Follow Back	X					X
Tobacco/Marijuana Use Questionnaire	X					
CBC, Hepatic panel, INR, Basic metabolic panel	X		X	X	X	X
Serum-WBC-endotoxin, FACS analysis of cell types, cytokines, oxidative stress markers, soluble CD14		X	X	X		
Plasma-Metabolomics		X	X	X		
Stool 16 multi-tag pyrosequencing (microbrome), fecal calprotectin		X	X	X		
Urine-Metagenome		X				

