### **Subject Disposition**

Missing values will be explained in individual data tables. No procedures for replacing missing values by estimates will be implemented.

If there is scientific evidence or explanation for one or more outliers, this will be presented together with a statistical test for outlier identification. In case of outliers, the corresponding statistical analysis will be provided with and without these values.

Any deviation from the original statistical plan will be described and justified in the study report.

**Primary endpoint:** The incidence and severity profile of adverse events will be reported for those receiving Imm-124 versus placebo. It is expected that there will be no signals for increased adverse events with Imm-124. The adverse event rates will be enumerated for each group. Proportions of subjects with specific adverse events will be compared using Fisher Exact test. However, no formal hypothesis testing is planned as there is no basis to expect any changes across groups.

**Principal secondary endpoint:** The principal secondary endpoint will be the decrease in plasma LPS (endotoxin) levels (adjusting for baseline) as measured by analysis of covariance across the study groups. This was chosen based on the mechanism of action of Imm 124-E. The hypothesis is that both active-drug groups are superior to placebo. In prior studies, we have found the standard deviation of LPS levels to be 8-10%.

**Subgroup Analysis:** We will perform subgroup analysis based on gender, race, baseline MELD and SOFA scores, and presence or absence of encephalopathy. Given the overall sample size, we do not anticipate having enough power to do meaningful hypothesis testing. We will also do

a multivariable regression analysis of outcomes with these as covariates to determine if they have an independent impact on outcome, and to identify any interaction terms between these covariates and treatment arm. These are primarily designed for hypothesis generation.

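### The plan gives no Lille outcome to a subject who dies before the Day 7 bilirubin, so early deaths can tilt this exploratory endpoint towards the arm that has more of them; MELD, DF and liver-function change have a related gap

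*Combined protocol and SAP*

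**What the plan says.** The synopsis lists among its efficacy endpoints the "number of subjects meeting Lille failure criteria" at Day 7. Exploratory Endpoints and Analysis Population give the same endpoint as a proportion with a score above 0.45; in Analysis Population it reads "Proportion meeting Lille criteria for futility (Lille score > 0.45". Analysis Population introduces its list with "An intent to treat analysis will also be performed for the following endpoints".

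The study design section names the inputs to the score, including the "total bilirubin level on day 7 of therapy". In Table 2 the row "Assessment of Lille Score" is marked at Day 7 only.

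Subject Disposition says that missing values will be explained in individual data tables, and then: "No procedures for replacing missing values by estimates will be implemented".

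Exploratory Endpoints lists "Mortality at day 7, day 30, day 90 and day 180" as a separate item. The synopsis and Analysis Population list mortality from Day 30 onwards only. No section links death to the Lille endpoint.

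The same intent-to-treat list includes "Change in MELD score and discriminant function adjusting at day 7 and 30 for baseline values", and change in liver function on the same days. Under the Data Safety Monitoring Board heading, continuous variables at end of study are to be compared by ANCOVA adjusted for baseline. The study design section and Removal of Subjects both say that subjects who meet the Lille failure criteria are removed from the study.

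**The concern.** A subject who dies before Day 7 has the worst possible outcome but no score. Intent to treat says who is analysed; it does not say what value such a subject takes. The at-least-7-days rule under Subject Populations concerns the pathophysiology endpoint, so it does not settle the matter. Two literal readings remain: the subject stays in the denominator and is not counted as a failure, or the subject leaves the denominator. Either can make an arm with more early deaths look more steroid-responsive than it was, and the choice could be made after the results are known.

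The change scores have a related gap. A subject who has died contributes no MELD, DF or liver-function value, so the means describe measured survivors.

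The synopsis says that the trial is meant to assess dose response and which endpoints suit further work. A short-term efficacy signal that depends on an unstated convention serves that purpose poorly.

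**Working it through.** The documents state no expected rate or sample size for the Lille endpoint, so there is no figure to reproduce; Table 4 concerns endotoxin only.

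**Inputs from the documents**
- 22 subjects per arm (Determination of Sample Size).
- Six-month survival of about 25% with Lille above 0.45 and 85% below it (study design section).
- Mortality above 40% in severe AH, with no time horizon (Current Treatment).

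**Assumptions**
- Six-month mortality is 40%.
- Deaths before Day 7 resemble six-month deaths in their Lille status.
- One arm has k = 1 to 4 deaths before Day 7 and the other has none. No Day 7 death rate is given.
- The true failure rate is the same in both arms.

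**Step 1. Effect of one death.** If the subject stays in the denominator as a non-failure and would otherwise have failed, the arm's rate falls by 1/22 = 4.5 points.

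**Step 2. Implied failure rate f.** 0.25f + 0.85(1 − f) = 0.60, so f = (0.85 − 0.60)/(0.85 − 0.25) = 41.7%, or 9.17 of 22.

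**Step 3. Share r of deaths that are Lille failures.** r = 0.75 × 0.417/0.40 = 78%. More generally r = 0.75f/(0.15 + 0.60f), which exceeds f for every f between 0 and 1. So the survival figures put failures disproportionately among the deaths whatever the failure rate.

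**Step 4. Apparent rate in the arm with k early deaths**, against 41.7% in the other arm:
- Non-failure among 22: (9.17 − 0.78k)/22
- Dropped: (9.17 − 0.78k)/(22 − k)
- Counted as failure: (9.17 − 0.78k + k)/22

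| k | Non-failure among 22 | Dropped | Counted as failure |
|---|---|---|---|
| 1 | 38.1% (−3.6) | 39.9% (−1.7) | 42.7% (+1.0) |
| 2 | 34.6% (−7.1) | 38.0% (−3.6) | 43.7% (+2.0) |
| 3 | 31.0% (−10.7) | 35.9% (−5.8) | 44.6% (+3.0) |
| 4 | 27.5% (−14.2) | 33.6% (−8.1) | 45.6% (+4.0) |

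Differences are in percentage points.

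**Step 5. Range for k = 2.** With a true failure rate of 25% to 50%, and 75% to 100% of deaths being would-be failures, the shift is −6.8 to −9.1 points if deaths are non-failures and −2.5 to −7.5 if they are dropped. If early deaths would have failed at the same rate as everyone else, dropping them gives no shift.

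**Step 6. Day 30 change scores.** At a failure rate of 41.7%, about 9 of 22 subjects per arm (22 × 0.417 = 9.2) would be removed at Day 7 as Lille failures. If removal ends follow-up, these living subjects also lack Day 30 values. The documents do not say whether it does.

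**The case against.** The strongest reply is that this is a gap in wording with limited consequences. Lille, MELD, DF and mortality are exploratory, the primary endpoint is safety, and the principal secondary endpoint is endotoxin. Mortality is reported separately and missing values must be explained, so early deaths would be visible. Entry rules cap MELD at 28 and exclude sepsis, active bleeding and raised creatinine, so deaths before Day 7 may be few. All of this stands and limits the weight of the point. It does not settle the denominator.

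Four stronger readings are tempting, and the documents do not support them.
- A reader might infer that the missing-value rule forbids counting a death as a failure. It bars estimates; classing death as failure is an endpoint definition. The plan omits that definition but does not prohibit it.
- A reader might infer that the bias always favours the arm with more deaths. If deaths are dropped, the direction depends on their unobserved Lille status. The 25% and 85% survival figures support that direction only if early deaths resemble six-month deaths.
- A reader might infer that several subjects per arm will be missing through death. The mortality figure has no horizon and describes severe AH generally, and listing Day 7 mortality as a time point gives no rate.
- A reader might infer that one or two deaths would produce a conclusive false finding. With 22 per arm, even 10/22 against 8/22 gives a two-sided Fisher p of 0.76. The effect is on the estimate and its interpretation.

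It can also be said that a composite mixes steroid response with death from any cause. That is a real cost, dealt with by showing the components.

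**Conclusion.** The point holds as a defect in the definition of exploratory endpoints. The plan requires a Day 7 value, gives death before Day 7 no outcome, and replaces nothing. If such deaths stay in the denominator as non-failures, each lowers the arm's Lille failure rate by up to 4.5 points. If they are dropped, the arm is favoured only if early deaths would have failed more often than survivors, which is likely on the protocol's survival figures but unproven. For two early deaths the illustrated shift is about 7 or 4 points; the number of deaths, the 40% six-month mortality and the likeness of early to six-month deaths are all assumed. When death counts as failure, the arm with more deaths no longer looks better.

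The change scores have the same weakness for deaths, and possibly a larger one at Day 30 from living subjects removed as Lille failures. The primary safety endpoint and the sample size are not affected. The change should be made because it is cheap and fixes the convention before results are seen.

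**What to change.** In Analysis Population, define the main Day 7 endpoint as a Lille score above 0.45 or death before the Day 7 bilirubin, with all randomized subjects in the denominator. Show by arm the two components and the number unscored for other reasons. Add a sensitivity analysis restricted to scored subjects.

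For change in MELD, DF and liver function at Days 7 and 30, keep the planned ANCOVA and add a rank-based comparison that gives deaths the worst rank. Report by arm how many subjects lack Day 30 values because of death and how many because of removal for Lille failure; the worst-rank analysis does not handle the second group, so the counts are needed to read it.

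Subject Disposition needs no exception, because these are outcome definitions and not estimates.

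The cost is wording and some extra tables, with no new data or visits. The drawback is that the main Day 7 endpoint is no longer the pure Lille proportion; the separate components keep that visible.

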## **Data Safety Monitoring Board**

An independent Data and Safety Monitoring Board (DSMB) to be established by the NIH and TREAT consortium to assess at intervals the progress of a clinical trial, the safety data, and the critical safety endpoints, and to recommend to the NIH whether to continue, modify, or stop a trial.

**Anticipated Outcomes:** Means for continuous variables at end of study will be analyzed adjusting for baseline values using ANCOVA. Proportions will be compared using chi square or Fisher's Exact test. We expect to show a greater decrease in mean circulating LPS levels in those receiving Steroids+ Imm 124-E compared to steroids + placebo. We further expect to demonstrate that those receiving Imm 124-E will have a reduction in MELD, DF, intestinal permeability, markers of intestinal inflammation, markers of dendritic cell activation, pro-inflammatory T-cell and cytokine profile, cholestasis (serum bile acids) and bilirubin.

**Additional pathophysiologic insights:** Microbiome-metagenomic-immunologic-transcriptomic-histologic data from will lend themselves to analyses using a "systems biology approach" to determine how interactions between these contribute to severe AH and how Imm 124-E can modify this. These will provide novel insights on the role of the metagenome in AH and provide additional targets for therapy in the future.

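### The exploratory day-7 Lille endpoint is compared only as an unadjusted proportion above 0.45, an inefficient comparison because five of its six inputs precede study drug

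*Combined protocol and SAP*

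**What the plan says.** - **Endpoint.** The Analysis Population section lists, for intent-to-treat analysis, "Proportion meeting Lille criteria for futility (Lille score > 0.45". The Exploratory Endpoints section places the same item, at day 7, under the words "The exploratory endpoints will include".
- **Test.** The Anticipated Outcomes paragraph, printed under Data Safety Monitoring Board, says: "Proportions will be compared using chi square or Fisher's Exact test". It names no covariate. For means of continuous variables the same paragraph prescribes ANCOVA on baseline.
- **Inputs.** The Overall Study Design and Plan section says the score uses age and, in its words, "at the start of therapy total bilirubin, albumin, creatinine, prothrombin time values and total bilirubin level on day 7 of therapy".
- **Neighbouring endpoints.** The same list in Analysis Population has "Change in liver functions adjusting for baseline values on day 7 and 30", and likewise adjusts MELD and discriminant function. The Lille item carries no such wording.
- **Data.** Table 2 schedules "CBC, Hepatic panel, INR, Basic metabolic panel" at screening and at day 7.
- **Regression.** The Subgroup Analysis paragraph adds a multivariable regression of unspecified outcomes on gender, race, baseline MELD, baseline SOFA and encephalopathy, for hypothesis generation.

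**The concern.** Two features of the planned comparison cost precision. Cutting the score at 0.45 treats a patient just above the line like one far above it. Leaving out baseline means that between-patient spread in five inputs, which study drug cannot change, enters the arm comparison as noise. The data to remove that noise are already collected, and the plan already uses the method for other endpoints.

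The synopsis says the study is meant to judge dose response and which endpoints suit later work. An insensitive comparison could make Lille, or a dose, look unpromising when it is not. Lille is also read before patients who fail it are removed from the study, so it escapes the attrition that affects later efficacy measures.

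**Working it through.** **The plan's own figure.** No power or failure rate is stated for Lille; the trial is sized on endotoxin. Table 4, Scenario 2 reproduces with n = 2(z₁₋α/2 + z_power)² × SD²/Δ² = 2 × (2.241 + 0.842)² × 25²/25² = 19.01, rounded up to the stated 20. The 22 per arm therefore says nothing about Lille.

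**Inputs.** From the documents: 22 per arm, two-sided 5%, six score inputs of which five are pre-treatment. Assumed, because the documents do not give them: failure of 40% on placebo and 20% on active, and the share R² of the score's variance explained by the pre-treatment inputs.

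**Model.** The Lille formula is not in the documents. I assume that on the log-odds scale the score is S = B + C, where B is the pre-treatment part (variance R²) and C the day-7 part (variance 1 − R²), independent and normal, with no missing values. Treatment shifts C only. Failure of 40% puts the cut at z = 0.253 and failure of 20% at z = 0.842, so the shift is δ = 0.588 SD.

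**Step 1: planned tests.**
- Chi-square: Φ[(0.20 − 1.96 × √(2 × 0.3 × 0.7/22)) / √((0.24 + 0.16)/22)] = Φ[(0.20 − 0.271)/0.135] = Φ(−0.525) = 30%. Exact enumeration also gives 30%.
- Fisher, exact enumeration: 21%.

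**Step 2: drop the cut, no adjustment.** Non-centrality 0.588 × √(22/2) = 1.95 on 42 df gives 48%.

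**Step 3: ANCOVA on B.** Non-centrality is δ/√(1 − R²) × √11 on 41 df. Simulation agrees within about one percentage point.

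| R² | δ/√(1 − R²) | Non-centrality | Power |
|---|---|---|---|
| 0.2 | 0.66 | 2.18 | 57% |
| 0.3 | 0.70 | 2.33 | 62% |
| 0.5 | 0.83 | 2.76 | 76% |
| 0.7 | 1.07 | 3.56 | 93% |

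With equal arms, ANCOVA rejects about 5% of the time. At 40% failure in both arms, chi-square rejects 4.7% and Fisher 2.2%.

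**Step 4: where the gain comes from.** Against chi-square, dropping the cut adds 18 points (30% to 48%). Adjustment then adds 9 points at R² = 0.2 and 28 points at R² = 0.5.

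**Step 5: other assumed rates.**

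| Failure | Fisher | Chi-square | Continuous, unadjusted | ANCOVA, R² 0.2 to 0.5 |
|---|---|---|---|---|
| 45% v 25% | 18.5% | 27-28% | 43% | 51-71% |
| 35% v 20% | 12.5% | 19.5% | 31.5% | 38-55% |

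Keeping the 0.45 cut but adjusting for B by logistic regression recovers only part of the gap: about 43% for 45% v 25% at R² = 0.5, against 71% for ANCOVA. Even that 43% is slightly flattering, because the test's null rejection rate was 5.6-7.8%.

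**The case against.** **The endpoint is exploratory.** This stands. No Lille power is claimed and no stated conclusion rests on it. A reader might infer that the trial fails in its purpose because it would probably miss a halving of Lille failure. The documents do not support that: the primary endpoint is safety, and the sample size is set on endotoxin.

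**Is most of the power discarded?** A reader might infer so, but it cannot be shown from the documents. Against chi-square, which the plan permits, power is halved only once R² reaches about 0.3 (30% v 62%); at R² = 0.2 chi-square keeps just over half (30% v 57%). Against Fisher the loss exceeds half throughout, but part of that is Fisher's conservatism. The limits of MELD 20-28 and creatinine 1.5 mg/dL may narrow baseline spread and lower R². The 93% figure needs a shift of more than one SD in the day-7 part within a week.

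**The day-7 data are already analysed.** This largely stands. Regressing B + C on arm and B gives the same arm coefficient as regressing C on arm and B. The planned baseline-adjusted day-7 liver-function change, if it includes bilirubin, therefore carries about the same power (57%, 63%, 76% and 93% at the four values of R²). It is nevertheless a separate endpoint, and the plan does not itemise its liver functions. The multivariable regression omits age and albumin and does not name Lille.

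**The 0.45 cut is the protocol's own failure rule.** This stands. A reader might infer that the proportion should become purely descriptive. That is a debatable trade-off, and the improvement does not need it.

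**Conclusion.** The planned Lille comparison is inefficient, and a better one needs no new data. For 40% v 20%, a baseline-adjusted ANCOVA would raise power from about 21% (Fisher) or 30% (chi-square) to about 57-76%. At low R² most of that gain comes from using the continuous score rather than from adjustment. ANCOVA was ahead of both planned tests at every pair of rates and R² shown. The size of the gap rests on assumed failure rates, R² of 0.2-0.5, a normal and additive log-odds score, and complete day-7 bilirubin. This is a worthwhile improvement to an exploratory analysis. It is not an error that undermines the trial's stated conclusions.

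**What to change.** 1. Keep the proportion above 0.45 with its planned chi-square or Fisher test.
2. Add to the Analysis Population list, labelled exploratory, an ANCOVA of the log-odds Lille score on arm with one covariate: the same score computed with day-7 bilirubin set equal to baseline bilirubin. Report each dose-versus-placebo difference with a 95% CI.
3. State which blood draw supplies the pre-treatment values. Table 2 has safety laboratory tests at screening but not at day 0, and patients may enter after fewer than 7 days of steroids.
4. Report, by arm, the number of patients without a day-7 bilirubin and why.

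The cost is a few lines of SAP text and code; no visit, sample or clinical rule changes. There are two downsides. The effect is on a score scale, so the proportion must stand beside it. Patients without a day-7 bilirubin, such as those who die before day 7, drop out of the ANCOVA because the plan allows no imputation. A binary failure endpoint could count such deaths, although the plan does not say whether it does.
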